6.9.3 Timing for Reporting of Adverse Events

The AEs occurring during the study must be documented, regardless of the assumption of a causal relationship. Adverse events should be documented from the time the subject receives the first dose of study medication until subject participation in the study has been completed. If a subject has 1 or more ongoing AEs at the time of study completion, the subject must be followed and provided appropriate medical care until the sign(s) and/or symptoms(s) of the AE have remitted or stabilized in the opinion of the Investigator.

When recording an AE, the following information should be provided on the study AE CRF:

1. Action Taken with Study Drug:

- None
- Investigational Product Discontinued
- Investigational Product Interrupted

2. Other Action Taken:

- None
- Non-Drug Therapy
- New OTC or Rx Drug Added
- Hospitalized less than 24 hours
- Hospitalized greater than or equal to 24 hours

3. Outcome of an adverse event is coded as:

- Fatal
- Not Recovered/Not Resolved
- Recovered/Resolved
- Recovered/Resolved with sequelae
- Recovering/Resolving
- Unknown/Lost to follow-up

6.9.4 Severity

Severity of an AE is defined as a qualitative assessment of the level of discomfort or the degree of intensity of an AE as determined by the Investigator or reported to him/her by the subject. The assessment of severity is made irrespective of study medication relationship or seriousness of the event and should be evaluated according to the following scale:

- 1 = Mild: present and noticeable, but not distressing, and no disruption of normal daily activities
- 2 = Moderate: bothersome, discomfort sufficient to possibly reduce or affect normal daily activity
- 3 = Severe: incapacitating, with inability to work or perform normal daily activity

A change in severity for a reported AE will require a stop date for the previous severity and a new start and stop date for the new severity. For example, a change in severity may go from mild to severe or from severe to moderate. In either case, the start and stop dates should be recorded.

Please note: a severe AE is not the same as a serious AE. Seriousness of an AE (NOT severity) serves as a guide for defining regulatory reporting obligations (see Section 6.9.8 for further information on serious AEs [SAEs]).

6.9.5 Relationship

The study medication relationship for each AE/adverse reaction should be determined by the Investigator using these explanations:

- **Not Related:** The event is clearly related to other factors such as subject's clinical condition; therapeutic interventions, concomitant disease or therapy administered to the subject and does not follow a known response pattern to the product.
- **Unlikely Related:** The event is most probably caused by other etiologies such as participant's underlying condition, therapeutic intervention, or concomitant therapy; or the delay between administration and the onset of the AE is incompatible with a causal relationship. Therefore, there is not a reasonable possibility that the AE was caused by the study medication.
- **Possibly Related:** The event follows a reasonable, temporal sequence from the time of study medication administration and/or follows a known response pattern to the study medication, but could have been produced by other factors such as the subject's clinical state, therapeutic interventions or concomitant therapy administered to the subject.
- **Related:** The event follows a reasonable, temporal sequence from the time of study medication administration and/or follows a known response pattern to the study

medication and cannot be reasonably explained by other factors such as subject's clinical state, therapeutic interventions or concomitant therapy administered to the subject, and either occurs immediately following study medication administration, or improves on stopping the study medication, or reappears on repeat exposure, or there is a positive reaction at the application site.

6.9.6 Expectedness

The most frequently reported AE for netarsudil ophthalmic solution in two Phase 2 and three Phase 3 studies (Clinical Study Reports [AR-13324-CS201](#), [AR-13324-CS202](#), [AR-13324-CS301](#), [AR-13324-CS302](#), and [AR-13324-CS304](#)) has been conjunctival hyperemia. Other AEs seen in greater frequency with netarsudil than in active control treatment arms in these studies include instillation site erythema or pain, eyelid erythema, conjunctival hemorrhage, conjunctival vascular disorder, blurred vision, corneal deposits, eye irritation, increased lacrimation, and foreign body sensation.

An AE or SAR is considered "unexpected" if it is not listed in the [Investigator's Brochure](#) or is not listed at the specificity or severity that has been observed. "Unexpected," as used in this definition, also refers to AEs or SARs that are mentioned in the Investigator's Brochure as occurring with this class of drugs or as anticipated from the pharmacological properties of netarsudil, and are not specifically mentioned as occurring with the IP. The AEs that are both unexpected and serious should be reported in an expedited fashion to the Sponsor (see Section 6.9.8 for further details).

6.9.7 Clinical Laboratory Adverse Events

Clinical laboratory values (other than pregnancy test results) that are noted as abnormal and clinically significant at study exit and that are changes from Visit 1 (Screening) values will be documented as AEs.

6.9.8 Serious Adverse Events or Serious Suspected Adverse Events

An Investigator must immediately report any SAE or SSAR (see Section [6.9.2](#) for definitions) to the Sponsor or Sponsor representative (contact information below), whether or not the SAE or SSAR is considered drug-related, including those listed in the protocol or Investigator's Brochure. The Investigator report must include an assessment of whether there is a reasonable possibility that the drug caused the event. The Investigator must report any SAE or SSAR that occurs during the study for a subject or any SAE or SSAR that occurs within 4 weeks (i.e., 30 days) after the last administration of study medication. Study endpoints that are SAEs (e.g., all-cause mortality) must be reported in accordance with Section 6.9.2 of the protocol unless there is evidence suggesting a causal relationship between the drug and the event (e.g., death from anaphylaxis). In that case, the Investigator must immediately report the event to the Sponsor or Sponsor representative. In case of incomplete information, the Investigator must provide follow-up information as soon as possible, again using the SAE report form.

In addition, in the case of immediately life-threatening AEs or AEs with fatal outcome, or AEs that are serious, unexpected (i.e., not in the Investigator's Brochure) and judged related to the study medication, the Investigator must inform the Sponsor or Sponsor representative by phone within 24 hours of notification or occurrence of the SAE.

Pregnancies occurring in subjects enrolled in the study or in their partners must be reported and followed to outcome. While pregnancy itself is not considered to be an AE or SAE, pregnancy reports are tracked by the Sponsor or Sponsor representative. Premature terminations including miscarriage, spontaneous abortion, or elective termination of a pregnancy for medical reasons will be reported as an SAE. Other pregnancy complications should be reported as SAEs, if they meet serious criteria. Should the pregnancy result in a congenital anomaly or birth defect, a separate SAE report must be submitted. Furthermore, all neonatal deaths that occur within 30 days of the birth should be reported as SAEs, without regard to causality.

The Investigator must complete the pregnancy report form and fax or email the form to the Sponsor or Sponsor representative within 1 business day of knowledge of the pregnancy. Following delivery or termination of pregnancy, the pregnancy report form is to be completed and submitted by fax or email to the Sponsor or Sponsor representative.

Pregnancies occurring up to 30 days after the last administration of study drug are to be reported.

Serious adverse events must be reported to the IRB according to the IRB requirements.

Important: The Investigator must report an SAE or SSAR occurring at his/her site to the Sponsor and IRB, regardless of causality.

Safety Email: [REDACTED]

Safety Fax: [REDACTED]

Medical Monitor/Sponsor Contact Telephone Number:

[REDACTED]

6.9.9 Follow-up of Subjects after Adverse Events

If an AE/adverse reaction occurs, the Investigator will institute support and/or treatment as deemed appropriate. If a serious or non-serious AE/adverse reaction is unresolved at the time of the last visit, efforts will be made to follow up until the AE/adverse reaction is resolved or stabilized, the subject is lost to follow-up, or there is other resolution to the event.

6.10 Concomitant Medication Assessments

Use of all medications should be documented on the appropriate CRF. The site staff responsible for recording all concomitant medications will be identified on the Delegation of

Responsibilities Log. Investigators are encouraged to contact the Sponsor/Sponsor representative for any questions regarding allowed medications. Judgment of continued study participation by the subject, and inclusion of this subject's subsequent visits in the safety and efficacy analysis will be made by the Sponsor.

6.11 Best Corrected Visual Acuity (BCVA)

Best corrected visual acuity (BCVA) will be taken at visits as a measure of ocular function and will be measured at screening and frequently throughout the study. Visual acuity will be measured using ETDRS charts or their equivalents. Accepted charts are those designed according to the principles described by Ferris and coworkers (Ferris 1982) and supported by the guidelines from the Eye Care Technology Forum (Ferris 1996).

See [Appendix 2](#) for details of the procedures to be followed when determining BCVA.

6.12 Biomicroscopy

Biomicroscopic examination of the eyelids, conjunctiva, cornea, anterior chamber, lens, iris, and pupil of both lenses will be carried out at every study visit for both eyes of subjects. Normal or abnormal status of these ocular tissues will be graded as described in [Appendix 2](#).

6.13 Gonioscopy/Pachymetry

Gonioscopy will be used to confirm the iridocorneal angle is open and to what extent. Eligible subjects must have an angle of 3 or 4 (Shaffer grading scale; [Stamper 2009](#)) for participation in the study. Gonioscopy may be performed up to 3 months prior to randomization. Pachymetry will be used to measure the thickness of the central cornea. Both of these assessments will be done in order to determine the eligibility of a subject to be enrolled in this study. Further information on these procedures is found in [Appendix 2](#).

6.14 Visual Field Testing

Visual field testing must be performed in both eyes. Visual field testing may be performed up to 3 months prior to randomization. Visual fields must be determined as automated threshold perimetry (e.g., 30-2 or 24-2 Humphrey). SITA Standard is preferred, SITA fast is also allowed. Visual fields must be reliable, defined as those with a) fixation losses less than or equal to 33%, b) false positives less than or equal to 33%, and c) false negatives less than or equal to 33%. Visual fields fixation losses should not be rounded up to the next whole number value. **The gaze track and blind spot should be turned on for all visual fields assessments in order to calculate the fixation losses.** See [Appendix 2](#) for further information.

6.15 Dilated Ophthalmoscopy

A dilated funduscopy examination including evaluation of the retina, vitreous, macula, choroid, optic nerve, and vertical cup/disc ratio will be performed. See [Appendix 2](#) for

further information on scoring. Evaluation of vertical cup-disc ratio will be performed when ophthalmoscopy is performed.

6.16 Intraocular Pressure

Local anesthetic will also be applied in order to facilitate IOP measurements with the Goldmann Applanation Tonometer. Tonometer calibration on at least a monthly basis must be documented.

Two consecutive IOP measurements of each eye must be obtained. If the 2 measurements differ by more than 2 mmHg, a third measurement must be obtained. Intraocular pressure will be analyzed as the mean of 2 measurements or as the median of 3 measurements ([Sherwood 2006](#)).

Each Goldmann tonometry value is read as an integer. When calculating the mean or median, it is possible to have a fractional value; any non-integral mean or median IOP number will be reported to one decimal place. Note: For purposes of determining eligibility of subjects to be enrolled, any non-integral mean IOP number should not be rounded.

IOP should be measured by qualified individuals using a calibrated Goldmann applanation tonometer.

6.17 Study Eye Selection Process

Subjects must qualify in both eyes based upon IOP and ocular history for a subject who qualifies; the study eye will be the eye with the higher IOP at 08:00 hours on Visit 3. If both eyes have the same IOP at 08:00 hours on Visit 3, then the right eye will be the study eye. For each subject, BOTH eyes will be treated.

6.18 Removal of Subjects from the Study or Study Treatment

6.18.1 Completed Subject

A completed subject is defined as one who completes all 28 days of planned dosing and completion of the post-treatment follow-up day visit procedures.

6.18.2 Non-completing Subject

A non-completing subject is defined as one who exits the study by their own volition or at the discretion of the Investigator, the Medical Monitor, and/or the Sponsor Safety Officer. Any subject may decide to voluntarily withdraw from the study at any time without prejudice. In the event that discontinuation of treatment is necessary, the Investigator will make every attempt to complete all subsequent safety assessments listed for Visit 6.0 (Day 29) as well as dilated ophthalmoscopy.

The subject may also be discontinued from the study for the following reasons:

- **Lack of Efficacy** (as demonstrated by IOP measurements and Investigator decision that there is a risk of additional glaucomatous damage if the subject continues in the study).
- **Adverse Events** (AEs including, in the opinion of the Investigator, clinically relevant laboratory abnormalities and intercurrent diseases reported by the subject or observed by the investigator with documentation in the CRF).
- **Withdrawal of Consent**
- **Non-compliance** (e.g., non-adherence to scheduled follow-up visits or non-compliance with dosing)
- **Lost to Follow-up**
- **Disallowed Concurrent Medication**
- **Investigator Decision**
- **Protocol Deviation**
- **Death**
- **Other**

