5.8 Treatment Compliance

All subjects will be instructed on the importance of following the once-daily dosing regimen. Dosing should occur in the evening between 20:00 and 22:00 hours. As no commercially available method is readily available for direct, single-container monitoring of treatment adherence with multi-dose ophthalmic products, no formal measure of treatment compliance is planned. Subjects should be reminded at all visits to dose every evening. In addition, subjects will be provided with dosing reminders.

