9.2 Determination of Sample Size

Assuming a 2-sided test with $\alpha = 0.05$ and a common standard deviation (SD) of 3.5 mmHg at each time point yielding a common SD of 3.0 for the diurnal mean assuming a correlation among time points of 0.60, 49 ITT subjects per arm yields at least 90% power to demonstrate superiority of netarsudil (0.02% or 0.04%) to placebo in mean diurnal study eye IOP (average of 08:00, 10:00, and 16:00 hours) at the Week 4 visit assuming a difference of at least 2.0 mmHg in the mean diurnal IOP. The study will be considered a success and superiority of netarsudil to placebo will be concluded if the two-sided p-value ≤ 0.05 at

Week 4. With 60 ITT subjects per arm, each test has 95% power to demonstrate superiority of netarsudil (0.02% or 0.04%) to placebo.

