9.3 Analysis Populations

9.3.1 Intent-to-Treat (ITT) Population

The ITT population will include all randomized subjects who have received at least 1 dose of study medication. This population will be the primary population for efficacy analyses and will be used to summarize all efficacy variables and will summarize subjects as randomized.

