9.3.2 Per Protocol (PP) Population

The per protocol (PP) population is a subset of the ITT population, which will include those subjects who do not have major protocol violations likely to seriously affect the primary outcome of the study as judged by a masked evaluation prior to the unmasking of the study treatment. This population will be the secondary population for efficacy analyses and will be used to summarize a subset of efficacy variables. If the PP and ITT populations are exactly the same, then additional efficacy analyses on the PP population will not be performed. The PP population will summarize subjects as treated.

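### Protocol 6.18.2 allows removal from the study for missed dosing or any protocol deviation, which can cost Week 4 IOP data that could still be collected and move the ITT estimate toward compliers

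*Protocol*

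**What the plan says.** Protocol 6.18.2 introduces its list with "The subject may also be discontinued from the study for the following reasons". The list includes protocol deviation, with no threshold of severity, and non-compliance, with the examples "non-adherence to scheduled follow-up visits or non-compliance with dosing". Adverse events, lack of efficacy, disallowed medication and investigator decision are separate entries.

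After discontinuation of treatment, 6.18.2 asks for the safety assessments of Visit 6.0. Protocol 3.1, 6.18.3 and 7.4 ask for every effort at a final visit with the Visit 6.0 examinations. Visit 6.0 is the 08:00 visit; the 10:00 and 16:00 readings belong to Visits 6.1 and 6.2 (Protocol 7.3.10 to 7.3.12, Appendix 1). No section asks for attendance through Week 4 after removal.

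On analysis, Protocol 9.3.1 says the ITT population "will be used to summarize all efficacy variables and will summarize subjects as randomized". The per-protocol population in 9.3.2 is limited to "those subjects who do not have major protocol violations likely to seriously affect the primary outcome of the study", judged under masking. Protocol 5.8 says "no formal measure of treatment compliance is planned". Protocol 9.5.2 planned multiple imputation; SAP 8.1.1 and 8.3.1 replace it with observed data only and no statistical inference, after early closure with about 10 ITT subjects per arm expected (SAP 8.2).

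**The concern.** A subject who misses doses or breaches a procedure can usually still have IOP measured. Ending follow-up for that reason turns an outcome that could be observed into a missing one, and the missingness is tied to how well the subject took the drug. The per-protocol population already exists to deal with deviations, so removal adds nothing to that analysis and takes data from the ITT analysis. The decision also rests on reported missed doses and judgement, since compliance is not formally measured.

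At stake is what the Week 4 difference means. If removed subjects benefit less than those who stay, the estimate describes a better-dosing subset of the active arm and is larger than the difference between the groups as randomized.

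**Working it through.** **1. The plan's own figures.** Protocol 9.2 takes SD 3.5 mmHg per time point, "yielding a common SD of 3.0 for the diurnal mean assuming a correlation among time points of 0.60", a 2.0 mmHg difference and two-sided 0.05, and states that "49 ITT subjects per arm yields at least 90% power".

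- SD of the diurnal mean: 3.5 × √((1 + 2 × 0.60)/3) = 2.997, which agrees with 3.0.
- Power by noncentral t with SD 3.0: 89.8% at 48 per arm, 90.4% at 49, 95.2% at 60. The stated 90% and 95% reproduce.

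**2. Whether a Week 4 value survives removal.** SAP 8.3 builds the diurnal mean from three readings. SAP 8.1.2 assigns early-termination IOP to the nearest visit, with a Week 4 window of 29 ± 3, that is Days 26 to 32.

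- Removed at or soon after Week 1 or Week 2, with the exit visit before Day 26: no Week 4 reading.
- Exit visit on Days 26 to 32: an 08:00 reading may exist. The SAP does not say whether one reading can stand for the three-reading mean.
- Missed doses reported only at Visit 6.0: the subject is already attending Week 4, so nothing need be lost.

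**3. Whether the analysis recovers it.** Under the SAP, a subject without a Week 4 mean is absent from the ANCOVA. Under Protocol Appendix 7, the imputation model holds treatment, baseline IOP and IOP at the given time point, with no term for compliance or reason for exit. Missing values are then in effect predicted from same-arm subjects with similar baseline who stayed. Both approaches target the effect in those who stayed.

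**4. Size under stated assumptions.** The documents give no removal rate, so f and e are assumed. Let f be the share of an active arm removed, e the true effect in them, and 2.0 mmHg the effect in the rest. Assume any placebo removals do not change the placebo mean.

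As-randomized effect = (1 − f) × 2.0 + f × e; overstatement = f × (2.0 − e).

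| f | As randomized, e = 0 | Overstatement | As randomized, e = 1.0 | Overstatement |
|---|---|---|---|---|
| 5% | 1.90 | 0.10 | 1.95 | 0.05 |
| 10% | 1.80 | 0.20 | 1.90 | 0.10 |
| 20% | 1.60 | 0.40 | 1.80 | 0.20 |

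Protocol 4.1 enrols 60 per arm against 49 required, an allowance of 11/60 = 18.3% for non-completers and disqualifications. If all of that allowance were used by such removals, power stays at 90.4% (49 per arm), but the overstatement would be 0.183 × 1.0 = 0.18 to 0.183 × 2.0 = 0.37 mmHg. The allowance protects power; it does not correct the change of target.

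**5. Against the precision available.** With SD 3.0 and 10 per arm, SE = 3.0 × √(2/10) = 1.34 mmHg. The 95% half-width is about 2.10 × 1.34 = 2.8 mmHg, and power for 2.0 mmHg is about 29%. One removed subject is 10% of an arm; with e = 0 that is 0.20 mmHg, or 0.20/1.34 = 0.15 SE. The top of the range is 0.40/1.34 = 0.30 SE.

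**The case against.** Several objections have force.

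- Removal is permitted, not required. Its rate, the effect in those removed and any imbalance between arms are all assumed. An effect of 0 describes a subject who would get no benefit at all from treatment, not one who missed some doses. A subject removed for an out-of-window visit may have the full effect, and then only precision is lost.
- The SAP already labels the analysis as informational and draws no inference, so a confirmatory claim is not at risk.
- Week 1 and Week 2 readings of removed subjects still enter the planned ITT MMRM, which can recover part of the information. It is a secondary analysis and does not replace the Week 4 ANCOVA.
- Continued follow-up is not free of difficulty. Previously treated subjects are washed out (Protocol 5.7.1) and other ocular hypotensive therapy is barred (5.6). A persistently non-dosing subject kept to Week 4 is either without effective therapy or on therapy that changes the meaning of the reading. Protocol 10.8 also counts as significant some deviations that bring added risk to the subject.

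The last objection limits the remedy: continued measurement must be conditional on safety and willingness, and the exit reasons cannot simply be struck out. The others limit the size. None supplies the missing Week 4 mean.

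A reader might go further and infer that hyperemia, which Protocol 1.3 expects on netarsudil, drives missed doses and so concentrates removals in the active arms. No section links hyperemia to dosing, and intolerance has its own exit reason. The imbalance is possible but undocumented.

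**Conclusion.** The point holds as a design weakness of uncertain and probably modest size. The removal rule can create missing ITT outcomes that were avoidable, and neither the SAP's observed-data ANCOVA nor the protocol's imputation restores them.

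The 0.05-0.40 mmHg range rests on three assumptions: 5-20% of an active arm removed, an effect of 0-1.0 mmHg in them against 2.0 mmHg in the rest, and no shift in the placebo mean. At about 10 per arm it is at most 0.30 SE. At the planned 60 per arm, SE = 3.0 × √(2/60) = 0.55 mmHg, and the same 0.40 mmHg would be 0.40/0.55 = 0.73 SE, so the rule matters more for a full-size trial.

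The documents do not support reading this as a demonstrated bias in the reported difference, or as a claim that every removed subject is lost to the Week 4 analysis.

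**What to change.** In Protocol 6.18.2 and 6.18.3, separate leaving the study from deviating from it. SAP 5.1 already summarizes reasons for subject discontinuation and for test agent discontinuation. State that:

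- dosing non-compliance or a protocol deviation is not by itself a reason to end outcome collection;
- such subjects, if willing and if the investigator sees no safety reason to exit them, are asked to attend the remaining scheduled visits through Week 4, with IOP at 08:00, 10:00 and 16:00;
- these values enter the ITT analysis as randomized;
- the deviation itself is handled in the masked per-protocol review.

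Leave the safety-related exit reasons and all treatment decisions as they are. Keep the reason categories in SAP 5.1: they report disposition, and deleting them would hide the attrition in question. Show the number removed for each reason, by arm, beside the Week 4 estimate.

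The cost is a short amendment, a few visits already in the schedule, and an ITT difference that may be slightly smaller. The protocol change cannot help subjects who have already exited after the early closure; for them only the reporting by arm and reason remains useful.
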